# 1.2 Rationale

The aim of this study is to assess immunogenicity and safety of different formulations of the adjuvanted quadrivalent cell-based (aQIVc) vaccine versus the non-adjuvanted quadrivalent cell based influenza (QIVc) vaccine.

Immunogenicity and safety will be assessed in the overall study population (adults  $\geq$ 50 years and above) and in the age subgroups  $\geq$ 50-64 years and  $\geq$ 65 years to determine the appropriate age population for this vaccine. Data from this study will be used to select the optimal dose to be tested in the pivotal Phase 3 immunogenicity and safety study in older adults.

# **1.3** Potential Risks and Benefits

Subjects will be exposed to aQIVc or QIVc vaccines.

As with all injectable vaccines, immediate systemic allergic reactions to vaccination can occur. The reactions for anaphylaxis are sporadic and estimated to be 1.3 per million vaccine doses administered for all vaccines (McNeil 2019). As a precautionary measure, all subjects will remain under observation at the study site for at least 30 minutes after vaccination. Vasovagal syncope (fainting) can occur before or after any vaccination, is usually triggered by the pain or anxiety caused by the injection and is not related to the substance injected. Therefore, it is important that standard precautions and procedures be followed to avoid injury from fainting. Intramuscular vaccination commonly precipitates a transient and self-limiting local inflammatory reaction. This typically includes injection site pain, erythema (redness), or induration (hardness).

aQIVc is expected to provide benefit over QIVc influenza vaccines in older adults by the inclusion of the MF59 adjuvant as well as the use of antigens produced in cell culture that more closely resemble the wild-type strains (Hedge 2015; Lambert et al. 2010). In addition, results of a dose-finding study with different dosages of antigen and adjuvant for the egg-based adjuvanted trivalent influenza vaccine (aTIV) indicate that the increase of the antigen and MF59 dose may be associated with a higher antigen-specific immune response (Otten et al. 2020). As such, optimization of the aQIVc vaccine composition may provide additional benefits for the older adult population.

Overall, the clinical safety experience with aQIV, different formulations of aTIV, and QIVc in older adults, in conjunction with data from the repeat dose aQIVc toxicology study are sufficient to support the initiation of this Phase 2 study, looking at the safety and immunogenicity of various aQIVc formulations in adults 50 years and older. In the repeatdose toxicity study, three doses of aQIVc, containing HA/dose ( HA/strain), were administered by intramuscular injection to male and female rabbits at 3-week intervals. The vaccine was immunogenic and there was no evidence of local or systemic toxicity. The most common local and systemic reactions observed in the egg-based formulation of the adjuvanted vaccine (aQIV) in older adults were injection site pain, headache, and fatigue. Most reactions were reported as mild or moderate in intensity. The most common local and systemic reactions associated with administration of the QIVc comparator vaccine in older adults included injection site pain, erythema, induration, headache, fatigue, and myalgia. Most reactions were reported as mild or moderate in intensity. In the dose-finding study with aTIV, the different formulations were all generally well tolerated. The incidence of solicited adverse events (AEs) was higher in subjects who received the highest dosages of MF59, but there were no apparent trends observed in terms of the incidence of unsolicited AEs. The solicited adverse reactions associated with the higher dosages of MF59 were mostly mild to moderate in severity. MF59 typically increases local reactogenicity in older individuals, which may reflect the enhanced immune response due to the adjuvant. Increasing dosages of MF59 did not appear to result in an increase in systemic solicited AEs, with the possible exception of fatigue (Otten et al. 2020).

Because most of the various formulations of the investigational vaccine (aQIVc) have never been administered to humans, additional safety precautions have been incorporated in this study (see Section 3.8, Stopping/Pausing Guidelines and Internal Safety Team).

Please refer to the current Investigator's Brochure (IB) for aQIVc for a summary of potential risks and benefits of aQIVc and to the Product Information for QIVc for a summary of potential risks and benefits of QIVc.

# **2** STUDY OBJECTIVES

# 2.1 Primary Objective

# 2.1.1 Primary Immunogenicity Objective

1. To assess the immunogenicity of the different aQIVc formulations in comparison with the non-adjuvanted QIVc vaccine as measured by hemagglutination inhibition (HI) assay\* at 28 days after vaccination.

\* In case of lack of agglutination for a specific strain using HI assay, immunogenicity for that strain will be assessed as measured by microneutralization (MN) assay as an acceptable alternative.

# 2.1.2 Primary Safety Objective:

- To assess the reactogenicity of all aQIVc formulations and the comparator, QIVc, for 7 days after vaccination.
- 2. To assess the safety of all aQIVc formulations and the comparator, QIVc, for 28 days after vaccination.

For primary endpoints, refer to Section 8.1.1, Primary Endpoints.

# 2.2 Secondary Objectives

# 2.2.1 Secondary Immunogenicity Objective(s)

- 1. To assess the immunogenicity of the different aQIVc formulations in comparison with the QIVc vaccine as measured by HI assay\* at 180 days after vaccination.
- 2. To assess the immunogenicity of the different aQIVc formulations in comparison with the QIVc vaccine as measured by MN assay at 28 and 180 days after vaccination.

\* In case of lack of agglutination for a specific strain, immunogenicity for that strain will be assessed as measured by MN assay as an acceptable alternative.

For secondary immunogenicity endpoints, refer to Section 8.1.2.1, Secondary Immunogenicity Endpoints.

#### 2.2.2 Secondary Safety Objectives

1. To assess the safety of all aQIVc formulations and the comparator, QIVc for 180 days after vaccination.

For secondary safety endpoints, refer to 8.1.2.2.

# 2.3 Exploratory Objectives

#### 2.3.1 Exploratory Immunogenicity Objectives

- To assess the immunogenicity of the different aQIVc formulations in comparison with the QIVc vaccine as measured by MN assay using heterologous target viruses at 28 days after vaccination in a subset of collected samples.
- 2. Additional exploratory immunogenicity analyses may be conducted to further characterize the immune response of the study vaccines.

For exploratory endpoints, refer to Section 8.1.3, Exploratory Endpoints.

The results of these exploratory analyses may be presented in an addendum to the Clinical Study Report (CSR).

# **3 STUDY DESIGN**

# 3.1 Overview of Study Design

Experimental design: This is a Phase 2, randomized, stratified, observer-blind, antigen and adjuvant dose-ranging clinical study in approximately 800 male and female adults aged 50 years and older (approximately equally split between two age groups;  $\geq$ 50-64 and  $\geq$ 65 years of age) who are healthy or have co-morbidities which increase their risk of complications from influenza infection.

Duration of the study: The study duration is approximately 6 months for each subject. The study will be conducted in one single influenza season.

Vaccination schedule: Single vaccination (Day 1).

Investigational Vaccine: The study will use 7 investigational formulations of aQIVc (see Table 3-1)

Comparator Vaccine: The study will use 1 comparator vaccine (see Table 3-1)

Treatment groups: All treatment groups will include approximately 100 subjects aged  $\geq$ 50 years of age (see Table 3-1). All subjects will receive one dose of study vaccine at Day 1. The aQIVc formulation numbers correspond to the design space as presented in Figure 3-1. Not all formulations within the design space will be directly evaluated in this study, but the study results will make it possible to model the effect of the non-tested formulations within the design space.

Group	Vaccine	Type of vaccine	HA antigen content/ strain (μg)	MF59 squalene content (mg)	Total injected volume (mL)	Number of randomized subjects
Α	aQIVc 1	Investigational				100
В	aQIVc 3	Investigational				100
С	aQIVc 6	Investigational				100
D	aQIVc 7	Investigational				100
Е	aQIVc 9	Investigational				100
F	aQIVc 10	Investigational				100
G	aQIVc 11	Investigational				100
Н	QIVc	Comparator	15	0	0.5	100

#### Table 3-1: Overview of study vaccines

The treatments for Groups B, C, D, E, F and G will be obtained by 'bed-side' mixing of QIVc, standard dose of aQIVc (formulation aQIVc 1) and MF59 solution. Mixing is not required for Groups Aand H.

#### Figure 3-1: Design Space

Randomization: an Interactive Response Technology (IRT) will be used in the study with stratification factors for age ( $\geq$ 50-64 and  $\geq$ 65 years of age) and history of any influenza vaccination within 3 previous years (yes/no) to randomly assign each subject to one of the 8 treatments.

Blinding: Observer-blind study.

Blood sample schedule: A blood sample will be collected from all subjects on Day 1 (prior to vaccination), Day 29 and Day 181.

Data collection: electronic Case Reporting Form (eCRF) and electronic Diary (eDiary).

Study periods: The study has a treatment period (Day 1 to Day 29) and a follow-up period (Day 30 to Day 181).

Study clinic visits: Three clinic visits for each subject: at Day 1, Day 29 and Day 181.

Safety phone call: Two safety phone calls (Day 7 and Day 91) will be conducted: on Day 7 to review the eDiary data as well as collect any unsolicited AEs, and their related medications and any vaccinations, and on Day 91 to collect only SAEs, medically attended adverse events

(MAAEs), AEs leading to withdrawal, and AESIs, and their related medications and any vaccinations.

Reactogenicity data collection: Solicited AEs, occurring at the day of study vaccination and the following 6 days (Day 1 through Day 7, or longer if the events are not resolved), will be recorded daily using an eDiary as completed by the subject. The qualified healthcare professional will separately evaluate the solicited systemic events and injection site pain during the Day 7 safety phone call.

Safety data collection: All unsolicted AEs will be collected for 28 days after vaccination. During the follow-up period (from 29 days after vaccination onwards), only unsolicited AEs will be collected that are SAEs, MAAEs, AEs leading to study withdrawal, and/or AESIs. These data will be captured by interviewing the subject during the clinic visits and safety phone calls and by review of available medical records. Subjects will be instructed to call the site in the event of any AE which they perceive as being of concern during the entire study period.

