# Table 0-1: Time and Event Schedule

Visit Type		Clinic Visit	Safety Phone Call	Clinic Visit*	Safety Phone Call	Clinic Visit*
Study Day		1	7	29	91	181
Vis	t Window (Days)	n/a	+3 day	-7/+3 days	+/-7 days	+/-14 days
	Visit Number	1	2	3	4	5
Study Event	References					
Screening and Randomization						
Informed Consent a	Section 5.1.1	Х				
Medical History b	Section 5.1.2	Х				
Physical Exam	Section 5.1.2	Х				
Targeted Physical Exam c	Section 5.4.1			Х		Х
Measuring body temperature	Section 5.1.2	Х				
Pregnancy test d	Section 5.1.2	Х				
Exclusion/Inclusion Criteria	Section 4	Х				
Randomization	Section 5.1.4	Х				
Study Treatment	· · · · · ·			•	•	
Vaccination	Section 5.2	Х				
Safety						
30 Minutes Post Injection Assessment	Section 5.3	Х				
Train and Dispense Subject eDiary	Section 5.3	Х				
Review of eDiary data and compliance	Section 3.6.2	On	going during eDiary	use		
Assess unsolicited AEs	Section 7.1.2	X	Х	X		
Assess SAEs	Section 7.1.4	X	Х	X	X	Х

Visit Type		Clinic Visit	Safety Phone Call	Clinic Visit*	Safety Phone Call	Clinic Visit*
	Study Day	1	7	29	91	181
Visit	t Window (Days)	n/a	+3 day	-7/+3 days	+/-7 days	+/-14 days
	Visit Number	1	2	3	4	5
Study Event	References					
Assess for AEs leading to withdrawal, medically attended AEs and AESIs	Section 7.1.4.1	Х	Х	Х	Х	Х
Assess relevant medications and vaccinations	Section 6.5	Х	Х	Х	Х	Х
Immunogenicity						
Serology blood draw Section 5.1.5		X e		Х		Х
Study End						
Study Completion/termination	Section 5.6					$\mathbf{X}^{\mathrm{f}}$

\* In the exceptional situation in which a clinic visit is not possible, such as in the case when a site is not able to see study subjects at the clinic due to local regulations related to the coronavirus pandemic, a home visit may be considered.

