# 5.4.1 Follow-up Clinic Visit

Post-vaccination clinic visits will be performed on Day 29 (visit 3), and at Day 181 (visit 5) (see Section 5.6, Study Completion Visit for assessments to be performed at Study Completion Visit). In the exceptional situation in which a clinic visit is not possible, such as in the case when a site is not able to see study subjects at the clinic due to local regulations related to the coronavirus pandemic, a home visit may be considered.

During the follow-up clinic visit on Day 29, the subject will be interviewed to determine if any unsolicited AEs occurred including SAEs, AESIs, MAAEs, and if any concomitant

medications or vaccines were taken/received in the time since the last contact. The qualified healthcare professional reviewing these data will discuss the symptoms (if any) reported by the subject and will determine if any additional diagnoses and/or AEs are present. Adverse events reported by the subject at this follow-up clinic visit must be recorded in the subject's source document and on an AE eCRF, as specified in Section 7.1, Safety Assessments.

If applicable, a qualified healthcare professional will perform a targeted physical examination if necessary based on specific complaints indicated by the subject.

The subject will be asked to return any electronic device that was provisioned for the collection of the solicited AEs, if applicable. If the eDiary application was installed on a personal phone, it will be removed. During the visit, approximately 10 mL of blood will be drawn from all subjects (see Section 3.7, Collection of Clinical Specimens).

In addition, the site should schedule the next study activity, a safety phone call on Day 91, with the subject. The subject will be reminded to contact the site if there are any questions and to contact the site immediately (or as soon as the subject is medically stable) if the subject has a medical condition that leads to hospitalization or an emergency room visit or has any other concern.

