### 5.4.2 Safety Follow-up Calls

Safety follow-up calls will be performed on Days 7 and 91.

Safety follow-up calls are calls made to the subject by a qualified healthcare professional designated on the site's roles and responsibilities log. These calls will follow a script as guidance, which will facilitate the collection of relevant safety information. The subject will be interviewed, and information relating to the following AEs will be collected:

Day 7 Safety Follow-up Call

- After review of the eDiary entries with the subject, the qualified healthcare professional will assess if any discrepancies exist (eg. presence/absence or severity) and if yes, make his/her own evaluation of the solicited systemic events and injection site pain in the relevant sections of the eCRF.
- All unsolicited AEs (including, but not limited to: SAEs, AESIs, MAAEs, and AEs leading to withdrawal)

• Concomitant medication associated with the events above or vaccinations.

Day 91 Safety Follow-up Call

- SAEs, AESIs, MAAEs, and AEs leading to withdrawal
- Concomitant medication associated with the events above or vaccinations.

Contact details including all safety information described by the subject must be written down in a designated location within the source document.

In addition, the site should schedule the next study activity with the subject. The subject will be reminded to contact the site if there are any questions and to contact the site immediately (or as soon as the subject is medically stable) if the subject has a medical condition that leads to hospitalization or an emergency room visit or has any other concern.

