# 5.6 Study Completion Visit

The study completion visit will occur on Day 181 and will be a clinic visit. In the exceptional situation in which a clinic visit is not possible, such as in the case when a site is not able to see study subjects at the clinic due to local regulations related to the coronavirus pandemic, a home visit may be considered. The date of study completion is the date of the last contact (clinic visit or telephone call) in which the subject's health status was assessed or, in cases where the subject does not agree to any further safety follow-up, it is the date consent is withdrawn. This date should be recorded at the end of Study eCRF page. For visit procedures to be performed for a subject whose planned study participation ends prematurely, please see Section 5.6.1, Early Termination Visit.

During the study completion clinic visit, the subject will be interviewed to determine if any SAEs, AESIs or MAAEs occurred and if any associated concomitant medications or vaccines were taken/received in the time since the last safety assessment. The qualified healthcare professional reviewing these data will discuss the symptoms (if any) reported by the subject and will determine if any additional diagnoses and/or AEs s are present. Adverse events reported by the subject at this follow-up clinic visit must be recorded in the subject's source document and on an Adverse Events eCRF, as specified in Section 7.1, Safety Assessments.

If applicable, a qualified healthcare professional will perform a targeted physical examination based on specific complaints indicated by the subject.

During the visit, approximately 10 mL of blood will be drawn from all subjects (see Section 3.7, Collection of Clinical Specimens).

The site will review with the subject the plan of when information relating to the subject's participation in the study may be available (e.g., study results, treatment assignments). It will also be discussed how information relating to the subject's participation in the study will be shared with the subject's healthcare provider if the subject chooses to share this information.

The site will complete the end of Study eCRF page and this will mark the completion of the subject's participation in the study.

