#### 7.1.2 Unsolicited Adverse Events

An unsolicited AE is an AE that was not solicited using a Subject eDiary and that was spontaneously communicated by a subject who was vaccinated with one of the study vaccines.

Potential unsolicited AEs may be medically attended (defined as symptoms or illnesses requiring hospitalization, or emergency room visit, or visit to/by a qualified healthcare professional), or were of concern to the subject. In case of such events, subjects will be instructed to contact the site as soon as possible to report the event(s). The detailed information about the reported unsolicited AEs will be collected by the qualified site personnel during the interview and will be documented in the subject's records.

The period of observation for AEs extends from the time the subject has received the study vaccine until the subject either completes the specified safety follow-up period (Day 181) or at early study termination.

All unsolicited AEs that start during the treatment period (Day 1 to Day 29) will be recorded in the eCRF. During the follow-up (Day 30 to Day 181), unsolicited AEs that meet any reporting criterion (an SAE, AESI, AE leading to withdrawal or a MAAE) are to be recorded in the eCRF.

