#### 8.1.1.2 Primary Safety Endpoints

- Solicited local or systemic AEs for 7 days following vaccination (Day 1 through Day 7), based on the subject reported data (eDiary).
- Severe solicited local or systemic AEs for 7 days following vaccination (Day 1 through Day 7), based on the subject reported data (eDiary).
- Unsolicited AEs for 28 days following vaccination (Day 1 to Day 29).
- SAEs, MAAE, AEs leading to withdrawal from the study, AESIs for 28 days after vaccination (Day 1 to Day 29).

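### A Visit 3 held on Day 22 to 28 leaves up to 7 of the 28 days of the primary unsolicited-AE endpoint without a full scheduled AE inquiry, and the SAP does not show it

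*Protocol*

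**What the plan says.** **Endpoint and recording rule.** Protocol section 8.1.1.2 lists as a primary safety endpoint "Unsolicited AEs for 28 days following vaccination (Day 1 to Day 29". Section 7.1.2 sets the matching rule: "All unsolicited AEs that start during the treatment period (Day 1 to Day 29) will be recorded in the eCRF".

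**Contacts that ask about every unsolicited AE.** In Table 0-1 the row "Assess unsolicited AEs" is marked at Visits 1, 2 and 3 only. Visit 3 is due on Day 29 with a window of 7 days before to 3 days after. At that visit, under section 5.4.1, "the subject will be interviewed to determine if any unsolicited AEs occurred including SAEs, AESIs, MAAEs".

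**Later contacts.** Section 3.1 describes the second phone call: "and on Day 91 to collect only SAEs, medically attended adverse events", with AESIs and AEs leading to withdrawal. Section 5.4.2 gives the same list for that call: "SAEs, AESIs, MAAEs, and AEs leading to withdrawal". At Day 181, section 5.6 says "the subject will be interviewed to determine if any SAEs, AESIs or MAAEs occurred"; Table 0-1 also marks AEs leading to withdrawal there.

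**Other routes.** Section 3.1 tells subjects to call the site about any AE that concerns them at any time in the study, and names review of available medical records. The eDiary prompts about unsolicited AEs in section 5.3.1 run from Day 1 to Day 7.

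**Analysis.** SAP section 8.8 assigns unsolicited AEs to the 28-day period by start date, and section 13.4 summarises them by period of onset. Neither refers to the date of Visit 3.

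**The concern.** The endpoint is defined by a fixed calendar window, while its capture depends on a visit that may be held up to a week before that window closes. A site can comply fully with the visit schedule and still not ask about the last days of the endpoint period.

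The error runs in one direction. An early visit can lose events. A late visit adds nothing to offset this, because an AE counts only if its onset is by Day 29.

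Nor would the planned output reveal the gap. The Unsolicited Safety Set (SAP section 7.5) admits any subject with a post-vaccination safety assessment, even the 30-minute one. Observation time (SAP section 9.1) runs to the last assessment, so a subject seen on Day 22 and again on Day 181 appears fully observed.

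At stake is whether the percentages labelled Day 1 to Day 29 mean what the label says. They belong to the Day 29 read-out, which Protocol section 8.6 says is meant to inform Phase 3.

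**Working it through.** The plan states no figure for this gap, so there is none to reproduce. The check is calendar arithmetic and a comparison of the contacts.

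**Inputs.** Visit 3 target Day 29, window -7/+3 days; second call Day 91, window +/-7 days (both Table 0-1). Endpoint period of 28 days after vaccination, ending on Day 29 (section 8.1.1.2).

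**Step 1: range of Visit 3.** Earliest 29 - 7 = Day 22. Latest 29 + 3 = Day 32.

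**Step 2: days without a full inquiry.** For a visit on Day v, the gap is max(0, 29 - v) days, and its share is the gap divided by 28.

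| Visit 3 on Day | Gap (days) | Share of 28 days |
|---|---|---|
| 22 | 7 | 25.0% |
| 23 | 6 | 21.4% |
| 24 | 5 | 17.9% |
| 25 | 4 | 14.3% |
| 26 | 3 | 10.7% |
| 27 | 2 | 7.1% |
| 28 | 1 | 3.6% |
| 29 to 32 | 0 | 0% |

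**Step 3: which AEs fall in the gap.** Take a Day 22 visit and an AE starting on Day 25.

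| Type of AE | Asked about later? |
|---|---|
| SAE, MAAE or AESI | Yes, at Day 91 and Day 181 |
| AE leading to withdrawal | Yes, at Day 91 (5.4.2) and Day 181 (Table 0-1) |
| Any other unsolicited AE | No |

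**Step 4: delay to the next scheduled contact.** After a Day 22 visit it is 84 - 22 = 62 to 98 - 22 = 76 days, and it uses the restricted list.

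**Step 5: average gap over subjects.** This needs the distribution of visit dates, which the documents do not give. As an assumption, let a share p of subjects be seen before Day 29, spread evenly over Day 22 to 28. Their mean gap is (7+6+5+4+3+2+1)/7 = 28/7 = 4 days, so the overall mean is 4p days.

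| p (assumed) | Mean gap (days) | Share of 28 days |
|---|---|---|
| 10% | 0.4 | 1.4% |
| 25% | 1.0 | 3.6% |
| 50% | 2.0 | 7.1% |
| 7/11 = 64% (even spread over Day 22 to 32) | 2.55 | 9.1% |

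Over all possible visit timings the mean lies between 0 and 7 days. These are days without a full inquiry, not lost events: the categories in the first two rows of step 3 are still asked for, and the documents give no onset rate for the rest.

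**The case against.** The case for leaving the plan alone has several parts.

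- **The remaining AEs are the minor ones.** Medically attended AEs, AESIs and AEs leading to withdrawal can be non-serious and are asked for later. A reader might infer that no contact after Visit 3 asks about any non-serious AE. The documents do not support that. This part stands and sets the limits of the point.
- **Other routes exist.** Subjects may call about any AE of concern, and section 5.4.1 has them reminded of this at Visit 3. Records are reviewed. Section 7.1.2 records by onset date, whenever the event is reported. At Day 181 any AE the subject mentions must be recorded (section 5.6). So it would be too strong to say these events cannot be captured. These routes are nevertheless weaker than a direct question, most of all for events that neither worry the subject nor lead to a visit.
- **The visit is aimed at Day 29.** Most visits may fall near the target, and subjects seen on Day 29 to 32 have no gap. This is fair: the even spread is only one assumption.
- **Comparisons between arms survive.** The window is the same in every arm, section 3.5 keeps subjects and investigators blinded, and the safety analysis is descriptive. Solicited reactions on Day 1 to 7 are untouched. This stands, and it removes any argument that the ranking of formulations is distorted.

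None of this closes the mismatch between the endpoint window and the visit window. The wider SAP window of -7 to +21 days does not close it either: it governs entry to the immunogenicity PPS (section 7.4), not AE collection.

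**Conclusion.** The point holds in a limited form. For subjects whose Visit 3 falls on Day 22 to 28, unsolicited AEs that are not SAEs, MAAEs, AESIs or AEs leading to withdrawal, with onset after the visit and by Day 29, are not asked for at any later scheduled contact. The primary 28-day percentages may be under-counted, and the SAP neither shortens the period nor flags these subjects.

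The size is 0 to 7 of 28 days per subject. The average depends on visit dates that the documents do not give; 2.55 days (9.1%) rests on an assumed even spread. A reader might take this as 9% of AEs lost, or as a demonstrated downward bias in every arm. Neither follows: the figure counts days, other routes may recover some events, and an arm in which nobody is seen early has no gap. Any under-count is probably similar across arms, so the concern is with absolute rates and their label rather than with comparisons between formulations.

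**What to change.** Reconcile the AE window with the visit window, in two parts.

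1. **Collection.** For any subject whose Visit 3 is before Day 29, add a scripted question at the next contact, the Day 91 call at the latest, about all unsolicited AEs with onset from that visit to Day 29. Record the answers in the AE eCRF. The cost is one question in an existing call. The limits should be stated: after a Day 22 visit the recall interval to the Day 91 call is 62 to 76 days, and events first elicited at that call enter only the second analysis, because the first uses data from Visit 1 to Visit 3 (Protocol section 8.6, SAP section 14).

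2. **Analysis at the Day 29 lock.** In SAP section 13.4, tabulate by arm the number of subjects whose last full AE inquiry was before Day 29. Then repeat the Day 1 to Day 29 unsolicited-AE summary in subjects whose Visit 3 was on or after Day 29. This uses visit dates already collected and costs one row and one repeated table. The repeat is descriptive and less precise. Under the even-spread assumption it would keep 4/11 of subjects, about 36 of 100 per arm.

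Part 2 matters more for the Phase 3 decision, because it works at the read-out that informs it and remains possible if the Day 91 calls have already been made.
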